13.6.1 Study recording period and follow-up for adverse events and serious adverse events

If a patient discontinues from treatment for reasons other than disease progression, and therefore continues to have tumor assessments, SAEs related to study treatment of procedures must be captured until the patient is considered to have confirmed PD and will have no further tumor assessments. The investigator is responsible for following all SAEs until resolution, until the patient returns to baseline status, or until the condition has stabilized with the expectation that it will remain chronic, even if this extends beyond study participation.

13.7 Relationship to protocol procedures

The Investigator is also required to provide an assessment of the relationship of SAEs to protocol procedures on the SAE report form. This includes both non-treatment—emergent (i.e., SAEs that occur prior to the administration of IP) and treatment-emergent SAEs. A protocol-related SAE may occur as a result of a procedure or intervention required during the study (e.g., blood collection). The following guidelines should be used by Investigators to assess the relationship of SAEs to the protocol:

- Protocol related: The event occurred due to a procedure or intervention that was described in the protocol for which there is no alternative etiology according to the patient's medical record.
- Not protocol related: The event is related to an etiology other than the procedure or intervention that
 was described in the protocol. The alternative etiology must be documented in the study patient's
 medical record.

13.8 Adverse events based on signs and symptoms

All AEs spontaneously reported by the patient or reported in response to the open question from the study personnel: "Have you had any health problems since the previous visit/you were last asked?" or revealed by observation will be collected and recorded in the CRF.

When collecting AEs, the recording of diagnoses is preferred, when possible, to recording a list of signs and symptoms. However, if a diagnosis is known and there are other signs or symptoms that are not generally part of the diagnosis, the diagnosis and each sign or symptom will be recorded separately.

13.9 Adverse events based on examinations and tests

The results from protocol-mandated laboratory tests and vital signs measurements will be recorded in the CRF. Deterioration as compared to baseline in protocol-mandated laboratory values and vital signs should therefore only be reported as AEs if they fulfill any of the SAE criteria or are the reason for discontinuation of study treatment.

If deterioration in a laboratory value or vital sign is associated with clinical signs and symptoms, the sign or symptom will be reported as an AE and the associated laboratory result or vital sign will be considered as additional information. Whenever possible, the reporting Investigator should use the clinical rather than the laboratory term (e.g., anemia versus low hemoglobin value). In the absence of clinical signs or symptoms, clinically relevant deteriorations in non-mandated parameters should be reported as AEs.

Deterioration of a laboratory value that is unequivocally due to disease progression should not be reported as an AE/SAE.

Any new or aggravated clinically relevant abnormal medical finding at a physical examination as compared with the baseline assessment will be reported as an AE.

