13.4 Safety parameters

13.4.1 Definition of adverse events (AEs)

The International Conference on Harmonization of Technical Requirements for Pharmaceuticals for Human Use (ICH) Guideline for Good Clinical Practice (GCP) E6(R2) defines an AE as:

Any untoward medical occurrence in a patient or clinical investigation patient administered a pharmaceutical product and which does not necessarily have a causal relationship with this treatment. An AE can therefore be any unfavorable and unintended sign (including an abnormal laboratory finding), symptom, or disease temporally associated with the use of a medicinal product, whether or not considered related to the medicinal product.

An AE includes but is not limited to any clinically significant worsening of a patient's pre-existing condition. An abnormal laboratory finding (including ECG finding) that requires an action or intervention by the investigator, or a finding judged by the investigator to represent a change beyond the range of normal physiologic fluctuation, should be reported as an AE.

AEs may be treatment emergent (i.e., occurring after initial receipt of investigational product) or nontreatment emergent. A non-treatment-emergent AE is any new sign or symptom, disease, or other untoward medical event that begins after written informed consent has been obtained but before the patient has received investigational product.

Elective treatment or surgery or preplanned treatment or surgery (that was scheduled prior to the patient being enrolled into the study) for a documented pre-existing condition, that did not worsen from baseline, is not considered an AE (serious or nonserious). An untoward medical event occurring during the prescheduled elective procedure or routinely scheduled treatment should be recorded as an AE or SAE. The term AE is used to include both serious and non-serious AEs.

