13.4.3 Definition of adverse events of special interest (AESI)

An adverse event of special interest (AESI) is one of scientific and medical interest specific to understanding of durvalumab and may require close monitoring. An AESI may be serious or non-serious. If the Investigator has any questions regarding an event being an immune-mediated AE (imAE), the investigator should promptly contact the Chief Investigator.

AESIs observed with durvalumab include:

- Diarrhea / Colitis and intestinal perforation
- Pneumonitis / ILD
- Hepatitis / transaminase increases
- Endocrinopathies (i.e. events of hypophysitis/hypopituitarism, adrenal insufficiency, hyper- and hypothyroidism and type I diabetes mellitus)
- Rash / Dermatitis
- Nephritis / Blood creatinine increases
- Pancreatitis / serum lipase and amylase increases
- Myocarditis
- Myositis / Polymyositis
- Neuropathy / neuromuscular toxicity (e.g. Guillain-Barré, and myasthenia gravis)
- Intestinal Perforations

Other inflammatory responses that are rare/less frequent with a potential immune-mediated etiology include, but are not limited to:

- Pericarditis
- Sarcoidosis
- Uveitis
- Other events involving the eye and skin
- Hematological events
- Rheumatological events
- Vasculitis
- Non-infectious meningitis
- Non-infectious encephalitis

It is possible that events with an inflammatory or immune mediated mechanism could occur in nearly all organs.

In addition, infusion-related reactions and hypersensitivity/anaphylactic reactions with a different underlying pharmacological etiology are also considered AESIs.

Further information on these risks (e.g. presenting symptoms) can be found in the current version of the durvalumab Investigator's Brochure. More specific guidelines for their evaluation and treatment are

described in detail in the Dosing Modification and Toxicity Management Guidelines (please see Appendix 1). These guidelines have been prepared by the Sponsor to assist the Investigator in the exercise of his/her clinical judgment in treating these types of toxicities. These guidelines apply to AEs considered causally related to the study drug/study regimen by the reporting investigator.

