14.3 Methods of statistical analyses

14.3.1 Safety analyses

The frequency and severity of AEs will be compared between the treatment arms using the Pearson's Chisquare and Fisher's exact test as appropriate.

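### Sections 13.4.1 and 13.9 conflict on when a laboratory abnormality is an AE, so the AE comparison in 14.3.1 depends on which rule a site follows

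*Protocol*

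**What the plan says.** Two sections of the protocol state when a laboratory abnormality becomes an adverse event.

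- **Section 13.4.1 (definition of AEs)** covers two kinds of finding: "An abnormal laboratory finding (including ECG finding) that requires an action or intervention by the investigator", and "a finding judged by the investigator to represent a change beyond the range of normal physiologic fluctuation, should be reported as an AE". It requires neither seriousness nor discontinuation, and it does not separate mandated from other tests.
- **Section 13.9 (AEs based on examinations and tests)** begins from data capture: "The results from protocol-mandated laboratory tests and vital signs measurements will be recorded in the CRF". It concludes that vital signs and mandated laboratory values that have deteriorated "should therefore only be reported as AEs if they fulfill any of the SAE criteria or are the reason for discontinuation of study treatment". Where symptoms are present, "the sign or symptom will be reported as an AE and the associated laboratory result or vital sign will be considered as additional information". If there are none, "clinically relevant deteriorations in non-mandated parameters should be reported as AEs".

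Section 14.3.1, the whole safety analysis section, says: "The frequency and severity of AEs will be compared between the treatment arms", by chi-square or Fisher's exact test. The synopsis speaks of toxicity classified by CTCAE v5.0. Neither place says whether laboratory values held in the CRF are graded and included.

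The schedule of assessments mandates haematology on days 1 and 10 of each chemotherapy course. Section 13.1 lists ALT, AST, bilirubin and creatinine among the chemistry tests.

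**The concern.** One laboratory result in one patient can be an AE under 13.4.1 and not an AE under 13.9. No order of precedence is given. A site could treat 13.9 as the specific rule for mandated tests, or 13.4.1 as the governing definition, and either choice would be reasonable.

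The comparison in 14.3.1 inherits this ambiguity. AE frequency and severity is a secondary endpoint (14.1), and section 4.4 describes finding out whether TRT adds side effects as an essential part of the trial. The DSMC review in 6.2 is written around SAEs, so non-serious laboratory toxicity has no other stated route to a comparison between arms. Both rules also leave room for judgement (whether a finding is beyond normal fluctuation, whether to stop treatment), and those making the judgement know the allocation.

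**Working it through.** The protocol states no figure on this point, so the main check is to set the passages side by side. A power illustration follows.

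**1. The same result under each rule.** Each case is asymptomatic, is not judged serious, and does not stop study treatment.

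| Result from a mandated test | Under 13.4.1 | Under 13.9 |
|---|---|---|
| Cytopenia that delays the next course or lowers its dose, as 8.2.5 suggests | AE: it required action | Not an AE |
| Isolated grade 3 ALT rise, bilirubin normal | AE if judged beyond normal fluctuation | Not an AE |
| Isolated grade 3 creatinine rise | AE if judged beyond normal fluctuation | Not an AE |

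**2. Other reporting routes.**
- *Seriousness (13.4.2).* The criteria go beyond hospitalisation. They include immediately life-threatening events and important medical events, and blood dyscrasias treated intensively without admission are among the examples. Some grade 4 values will qualify. Section 13.5.1 keeps severity apart from seriousness and says a grade 3 event need not be serious.
- *Potential Hy's Law cases (13.15.2).* These need ALT or AST at least 3 x ULN together with bilirubin at least 2 x ULN. Isolated transaminase rises, creatinine rises and cytopenias do not qualify.
- *AESIs (13.4.3).* The list includes "Hepatitis / transaminase increases" and creatinine increases, serious or not, and section 17 has AESI reports reviewed centrally. Section 13.9 does not exempt AESIs from its restriction, so whether such a rise is reported remains unclear.

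The affected group is therefore asymptomatic, non-serious grade 3-4 abnormalities in mandated tests that do not stop treatment.

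**3. Denominator.** Section 14.4 requires 128 per arm and allows 15% loss: 128 / 0.85 = 150.6, rounded up to 151 per arm, or 302 in total. This reproduces the planned enrolment. The safety set (14.2.1) is everyone who starts chemoimmunotherapy, so 151 per arm is an upper figure.

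**4. Illustration of under-capture (assumptions, not protocol figures).** The control rate of 62% is the grade 3-4 rate that section 4.5.2 cites for the reference regimen. The experimental rates of 70%, 75% and 78% are assumed. A share m of patients with grade 3-4 toxicity is missed equally in both arms, so the visible rates are a = 0.62(1 - m) and b = p(1 - m). With n = 151 and p̄ = (a + b)/2,

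power = Φ{ [ (b - a) - 1.96 √(2p̄(1 - p̄)/n) ] / √( [a(1 - a) + b(1 - b)]/n ) }.

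For p = 0.75 and m = 0: (0.130 - 1.96 × 0.0535) / 0.0529 = 0.48, so power is 68%. For m = 0.4 the visible rates are 0.372 and 0.450: (0.078 - 1.96 × 0.0566) / 0.0565 = -0.58, so power is 28%.

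| Share missed | 62% vs 70%: visible difference, power | 62% vs 75% | 62% vs 78% |
|---|---|---|---|
| 0% | 8.0 points, 31% | 13.0 points, 68% | 16.0 points, 86% |
| 20% | 6.4 points, 20% | 10.4 points, 44% | 12.8 points, 61% |
| 40% | 4.8 points, 13% | 7.8 points, 28% | 9.6 points, 39% |
| 60% | 3.2 points, 9% | 5.2 points, 17% | 6.4 points, 24% |

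The share missed is the product of two unknowns: the proportion of patients at sites that follow 13.9, and the proportion of grade 3-4 patients whose only grade 3-4 toxicity is of the affected kind. For example, 0.5 × 0.4 gives the 20% row. The protocol supplies neither.

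**The case against.** The strongest reply is that nothing is lost. Section 13.9 restricts AE reporting because mandated results are already in the CRF, which avoids double entry. The synopsis plans a comparison of toxicity by CTCAE, and an analysis plan that is not shown could grade the stored values. Section 13.4.1 would also bring in most findings that lead to action.

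Much of this stands. The values are kept, and a missing laboratory table would not by itself be a fault in the protocol. The rule for non-mandated tests is also consistent with that reasoning, since those results have no other place in the CRF. It should not be read as ranking trivial findings above serious ones.

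The conflict remains. What counts as an AE is a site reporting rule fixed in the protocol. An analysis plan can add a laboratory table, but it cannot make AE reports consistent once sites have followed different sections.

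A reader might infer more: that most grade 3-4 laboratory toxicity drops out of the comparison, or that the laboratory-type AESIs are removed from it. The protocol does not support either. It gives no laboratory-only share of toxicity, 13.4.1 points the other way, the seriousness criteria are broad, and AESI and Hy's Law reporting exist alongside 13.9. Nor does it show bias in favour of one arm. A site that applies one rule to all its patients would mainly dilute a true difference. Differential reporting is possible in an open-label trial but is not demonstrated.

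**Conclusion.** The point holds as a contradiction between two stated reporting rules, with a direct consequence for the only safety comparison described. Asymptomatic, non-serious grade 3-4 abnormalities in mandated tests enter that comparison or stay out of it according to the section a site follows. The protocol should be corrected here.

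The size is unknown. The power figures show that the loss would matter if the missed share were appreciable; they do not estimate that share. They assume equal capture in both arms and capture unrelated to grade, although worse grades are likelier to meet a seriousness or stopping criterion. They also take 62% as a true rate, although it cannot be seen here how that trial counted laboratory-only events.

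**What to change.** 1. Reconcile 13.4.1 and 13.9 so that one rule applies to mandated laboratory tests, and say how it applies to laboratory findings on the AESI list. Which reporting rule to keep is for the sponsor to decide.

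2. Add to 14.3.1, for example: *Mandated laboratory values recorded in the CRF are graded by CTCAE v5.0 where a grade exists, whether or not they were reported as AEs. The worst grade per patient and parameter is compared between arms and is included in the overall grade 3-4 rate.*

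The second change makes the laboratory part of the comparison independent of site reporting practice and uses data the trial already collects. It costs a short grading program. The downside is that reported grade 3-4 rates will be higher in both arms. No treatment rule changes.

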13.10 Disease progression

Disease progression can be considered as a worsening of a patient's condition attributable to the disease which is being studied. It may be an increase in the severity of the disease under study and/or increase in the symptoms of the disease. The development of new or progression of existing metastasis to the primary cancer under study should be considered as disease progression and not an AE/SAE. Events that are unequivocally due to disease progression should not be reported as an AE/SAE during the study.

13.11 New cancers

The development of a new cancer should be regarded as an SAE. New primary cancers are other cancers than SCLC that have been identified after the patient's inclusion in this study.

13.12 Deaths

All deaths that occur during the study treatment period, or within the protocol-defined follow-up period after the administration of the last dose of study drug, must be reported as follows:

- Death clearly resulting from disease progression should be reported to the Study Monitor/Physician at the next monitoring visit and should be recorded in the CRF. It should not be reported as an SAE.
- Where death is not due (or not clearly due) to progression of the disease under study, the AE
 causing the death must be reported to the Study Monitor/Physician as an SAE within 24 hours. It
 should also be recorded in the CRF.
- The report should contain a comment regarding the co-involvement of PD, if appropriate, and should assign main and contributory causes of death.
- Deaths with an unknown cause should always be reported as an SAE. It should also be recorded in the CRE
- A post-mortem may be helpful in the assessment of the cause of death, and if performed, a copy of the post-mortem results should be forwarded to the central trial office in Trondheim.

Deaths occurring after the protocol defined safety follow-up period after the administration of the last dose of study drug should be recorded in the CRF. If the death occurred as a result of an event that started after

the defined safety follow-up period and the event is considered to be due to a late onset toxicity to study drug, then it should also be reported as an SAE.

13.13 Reporting of serious adverse events and serious unexpected adverse reactions to the IRB and/or the Regulatory Authority

All SAEs must be reported, whether or not considered causally related to the investigational product. The Sponsor is responsible for informing the IRB and/or the Regulatory Authority of SAEs and SUSARs as per local requirements.

If any SAE occurs, investigators or other site personnel must inform appropriate Sponsor within one day i.e., immediately but no later than 24 hours of when he or she becomes aware of it.

For fatal or life-threatening adverse events where important or relevant information is missing, active follow-up is undertaken immediately. Investigators or other site personnel inform Sponsor representatives of any follow-up information on a previously reported SAE within one calendar day i.e., immediately but no later than 24 hours of when he or she becomes aware of it.

The reference document for definition of expectedness/listedness is the IB for durvalumab.

13.14 Reporting of serious adverse events to AstraZeneca

The central trial office in Trondheim is responsible for informing AstraZeneca (AZ) of SAEs. All SAEs have to be reported to AZ, whether or not considered causally related to durvalumab. SAEs related to durvalumab must be provided to AZ as individual case reports. SAEs unrelated to the durvalumab must be provided to AZ in quarterly reports.

At the end of the study a final summary listing of all SAEs notified to the regulatory authority and/or AZ during the study, must be provided to AZ to enable reconciliation of safety information held by AZ for durvalumab.

SAEs that do not require expedited reporting to the Regulatory Authority/IRB/IEC still need to be reported to AZ in quarterly reports.

Suspected Unexpected Serious Adverse Reactions (SUSARs) must be reported to AZ at the same time these events are notified to regulatory authorities.

13.14.1 Reporting of deaths to AstraZeneca

The central trial office will report all SAEs resulting in death or death of unknown cause to AstraZeneca via [contact] within 7 calendar days of awareness or sooner when required (See Section 13.13).

13.15 Other events requiring reporting

13.15.1 Overdose

An overdose is defined as a patient receiving a dose of durvalumab in excess of that specified in the Investigator's Brochure, unless otherwise specified in this protocol.

Any overdose of a study patient with durvalumab, with or without associated AEs/SAEs, is required to be reported within 24 hours of knowledge of the event to the sponsor. The sponsor must report these to AstraZeneca Patient Safety or designee using the designated Safety e-mailbox within 7 calendar days or sooner when required. If the overdose results in an AE, the AE must also be recorded as an AE. Overdose does not automatically make an AE serious, but if the consequences of the overdose are serious, for example death or hospitalization, the event is serious and must be recorded and reported as an SAE. There is currently no specific treatment in the event of an overdose of durvalumab. The investigator will use clinical judgment to treat any overdose.

13.15.2 Hepatic function abnormality

Hepatic function abnormality that fulfills the biochemical criteria of a potential Hy's Law case in a study patient, with or without associated clinical manifestations, is required to be reported as "hepatic function abnormal" within 24 hours of knowledge of the event to the sponsor. The Sponsor must report these

Study Number TRIPLEX
Protocol Version Number 1.1
Date 05-14N-2

Norwegian University of Science and Technology

events to AstraZeneca Patient Safety using the designated Safety e-mailbox within 7 calendar days or sooner when required, unless a definitive underlying diagnosis for the abnormality (e.g., cholelithiasis or bile duct obstruction) that is unrelated to durvalumab has been confirmed. The criteria for a potential Hy's Law case is Aspartate Aminotransferase (AST) or Alanine Aminotransferase (ALT) ≥3x Upper Limit of Normal (ULN) together with total bilirubin ≥2xULN at any timepoint during the study following the start of study medication irrespective of an increase in Alkaline Phosphatase (ALP).

- If the definitive underlying diagnosis for the abnormality has been established and is unrelated to durvalumab, the decision to continue dosing of the study patient will be based on the clinical judgment of the investigator.
- If no definitive underlying diagnosis for the abnormality is established, dosing of the study patient must be interrupted immediately. Follow-up investigations and inquiries must be initiated by the investigational site without delay.

Each reported event of hepatic function abnormality will be followed by the investigator and evaluated by the sponsor and AstraZeneca.

13.15.3 Pregnancy

Maternal exposure

If a patient becomes pregnant during study participation, study treatment should be discontinued immediately.

Pregnancy itself is not regarded as an AE unless there is a suspicion that the IP under study may have interfered with the effectiveness of a contraceptive medication. Congenital abnormalities or birth defects and spontaneous miscarriages should be reported and handled as SAEs. Elective abortions without complications should not be handled as AEs. The outcome of all pregnancies (spontaneous miscarriage, elective termination, ectopic pregnancy, normal birth, or congenital abnormality) should be followed up and documented even if the patient was discontinued from the study.

If any pregnancy occurs during the study, the investigator or other site personnel should inform the sponsor within 1 day, i.e., immediately, but no later than 24 hours of when he or she becomes aware of it.

The sponsor will work with the Investigator to ensure that all relevant information is provided within 1 to 5 calendar days. Sponsor must report to AstraZeneca Patient Safety using the designated Safety e-mailbox within 7 calendar days or sooner when required, for pregnancies with SAEs and within 30 days for all other pregnancies. The same timelines apply when outcome information is available.

Paternal exposure

Male patients should refrain from fathering a child or donating sperm during the study and for 180 days after the last dose of durvalumab + any drug combination therapy or 90 days after the last dose of durvalumab monotherapy, whichever is the longer time period.

Pregnancy of the patient's partner is not considered to be an AE. However, the outcome of all pregnancies (spontaneous miscarriage, elective termination, ectopic pregnancy, normal birth, or congenital abnormality) occurring from the date of the first dose until 180 days after the last dose of durvalumab + any drug combination therapy or 90 days after the last dose of durvalumab monotherapy, whichever is the longer time period should, if possible, be followed up and documented.

Where a report of pregnancy is received, prior to obtaining information about the pregnancy, the investigator must obtain consent from the patient's partner. The local study team should adopt the generic ICF template in line with local procedures and submit it to the relevant IRB/REB/IEC prior to use.

